10.6.4. Efficacy and Health Outcomes

Spirometry

Predicted FEV1, Predicted FVC, Absolute and Percent Reversibility in FEV1, Percent Predicted FEV1, Percent Predicted FVC, and Pre-salbutamol and Post-salbutamol FEV1/FVC Ratio
 
 These derived items will be delivered in a dataset from the vendor for central spirometry, except for post-salbutamol FEV1/FVC ratio, and no recalculation will be performed. Post-salbutamol FEV1/FVC ratio will be calculated as the ratio of post-salbutamol FEV1 and FVC values.

Trough
 
 The trough value for FEV1 and FVC at Weeks 4, 12 and 24 is the value of the pre-dose assessment. If the actual time of assessment is after the time of dosing on that day, the value for FEV1 and FVC will not be used. Change from baseline in trough FEV1 and FVC will be calculated.

St. George's Respiratory Questionnaire for COPD Patients (SGRQ-C)
General

 • The SGRQ-C contains 14 questions with a total of 40 items grouped into three domains (Symptoms, Activity and Impacts). • The details for how to score the SGRQ-C are outlined in the SGRQ-C manual (Jones, 2016). This includes details on how to handle missing data. • SGRQ-C domain and total score will be converted to SGRQ scores as described in the manual. • Changes from baseline in domain and total score will be calculated for the converted scores. • If the language of the SGRQ-C conducted at a post-treatment visit is different to the language used at Day 1, all SGRQ scores at that visit and all subsequent visits will be set to missing.
Responder Status according to SGRQ Total Score

 • A subject will be considered a responder according to SGRQ total score if their on-treatment SGRQ total score has decreased at least 4 units from baseline SGRQ total score. • A subject will be considered a non-responder if their on-treatment SGRQ total score has decreased by less than 4 units, has not changed, or has increased compared to baseline. • Missing data will be handled as detailed in Section 10.7.2

COPD Exacerbations

 • Each COPD exacerbation will be categorized based on severity as follows: 
 ○ Mild: no treatment with systemic/oral corticosteroids and/or antibiotics and no hospitalization ○ Moderate: required treatment with systemic/oral corticosteroids and/or antibiotics (not involving hospitalization) ○ Severe: required in-patient hospitalization • The duration of the exacerbation will be calculated as (exacerbation resolution date or date of death - exacerbation onset date + 1). • The time to the first on-treatment exacerbation will be calculated as (exacerbation onset date of first on-treatment exacerbation – date of start of treatment + 1). • Subjects will be represented from their Week 0 date to the earliest of the event or censoring. For subjects who do not experience the event will be censored at the earliest of the date of their treatment stop date +1 day or the date of death.
Association to Chest Imaging (X-ray or CT Scan)

 • A chest X-ray or CT scan is considered associated with a moderate/severe exacerbation if it is performed within 0 to +14 days of the exacerbation start date.

SAC BDI/TDI
General

 • The BDI focal score will be calculated as the sum of the ratings recorded for each of the three individual scales (Functional Impairment, Magnitude of Task, Magnitude of Effort). Each of these scales has five possible scores ranging from 0 to 4 (with lower scores indicating more impairment), so the range of the BDI focal score is 0 to 12. If a score is missing for any of the three scales, then the BDI focal score will be set to missing. BDI is assessed at baseline (Week 0). • The SAC TDI focal score will be calculated as the sum of the ratings recorded for each of the three individual scales (Functional Impairment, Magnitude of Task, Magnitude of Effort). Each of these scales has a possible score ranging from -6 to +6. SAC TDI focal score is calculated as the sum of the three individual scores and then divided by 2 (so the range of the TDI focal score is -9 to +9). If a score is missing for any of the three scales, then the SAC TDI focal score will be set to missing. • If the language of the SAC TDI conducted at a visit is different to the language for the BDI, all TDI scores at that visit and all subsequent visits will be set to missing
Responder Status according to SAC TDI Focal Score

 • A subject will be a responder if the on-treatment SAC TDI focal score was at least 1 unit at that visit. • A subject will be considered a non-responder if their on-treatment SAC TDI focal score was less than 1 unit. • Missing data will be handled as detailed in Section 10.7.2

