12.7.1.1. COPD Exacerbation Severity

Each COPD exacerbation will be categorized based on severity as follows:

Mild: Worsening symptoms of COPD that are self-managed by the subject. Mild exacerbations are not associated with the use of corticosteroids or antibiotics.

Moderate: Worsening symptoms of COPD that require treatment with oral/systemic corticosteroids and/or antibiotics.

Severe: Worsening symptoms of COPD that require treatment with in-patient hospitalisation.

Every effort should be made to conduct a chest x-ray within 48 hours of identification of a moderate or severe exacerbation.

Details of an exacerbation should be recorded in the exacerbation page of the eCRF. However, exacerbations should not be recorded in the AE section of the eCRF unless they meet the definition of an SAE. (Pneumonia must be recorded in the AE or SAE section of the eCRF and on the Pneumonia page of the eCRF.)

Use of antibiotics for the treatment of upper or lower respiratory tract infections will not be considered a COPD exacerbation unless the subject experiences worsening symptoms of COPD which match the definition of an exacerbation as given above.

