12.7.1.7. Guideline for assessing exacerbations that increase in severity

If an exacerbation starts off as mild, but becomes moderate or severe or starts off as moderate and becomes severe, the exacerbation should be captured as one exacerbation and classified by its highest level of severity.

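### Exacerbation severity ignores fatal outcome: an untreated, non-admitted fatal exacerbation grades as mild and, if there was no earlier event, is censored in time to first moderate/severe exacerbation (minor)

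*SAP*

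**What the plan says.** SAP 10.6.4 puts each exacerbation in one of three severities. The lowest is "Mild: no treatment with systemic/oral corticosteroids and/or antibiotics and no hospitalization". Moderate means treated with steroids or antibiotics but not admitted. The highest is "Severe: required in-patient hospitalization".

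Protocol 12.7.1.1 grades on the same two criteria, with slightly different wording at the bottom, where a mild event is described as "Worsening symptoms of COPD that are self-managed by the subject". Its top level is "Severe: Worsening symptoms of COPD that require treatment with in-patient hospitalisation". For an event that worsens, Protocol 12.7.1.7 says that "the exacerbation should be captured as one exacerbation and classified by its highest level of severity", but the levels available are the same three. None of these definitions mentions a fatal outcome.

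For time to first on-treatment moderate/severe exacerbation, SAP 10.6.4 states: "For subjects who do not experience the event will be censored at the earliest of the date of their treatment stop date +1 day", or at death if that is sooner. SAP 8.1.2.4 fits a Cox model and Kaplan-Meier curves, treats withdrawal before an exacerbation as random censoring, and plans no competing-risk or sensitivity analysis for deaths.

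**The concern.** The severity rule and the censoring rule each look ordinary. Together they give a wrong answer in one situation. A subject who dies of an exacerbation before receiving steroids, antibiotics or a bed has had the worst possible outcome of the event under study, yet the rule grades it at the bottom of the scale. The analysis then treats the subject as event-free up to the point of censoring. Cox and Kaplan-Meier methods assume that censored subjects carry the same future risk as those still followed. A subject removed because the disease process killed them breaks that assumption.

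At stake are the validity of a pre-specified secondary endpoint in a few subjects and the severity split in the descriptive tables. If such a case arose with no rule in place, its class would have to be settled by judgement, possibly after unblinding.

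**Working it through.** **Tracing the rules.** Take a subject with an on-treatment exacerbation that ends in death.

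- *Admitted as an in-patient:* severe, counted as an event at onset. No problem.
- *Treated with steroids or antibiotics, not admitted:* moderate, counted as an event at onset. Only the label is affected.
- *No steroid, antibiotic or admission, but an earlier on-treatment moderate/severe event:* the earlier event is already the first event. The time-to-event result does not change.
- *No steroid, antibiotic or admission, and no earlier event:* mild, not an event, censored no later than death. This is the affected case. A death in the emergency room before admission could follow the same path, because SAP 8.1.1.2 reports emergency-room visits separately from hospitalisation.

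**The plan's own figures.** No event rate, event count, hazard ratio or power is stated for this endpoint. The only powered figure is 816 evaluable subjects for trough FEV1. It reproduces: 2 × (1.960 + 1.282)² × 220² / 50² ≈ 407 per arm, 814 in total. Nothing here changes it.

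**Size.** Inputs:

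- N = 398 + 252 + 215 + 194 = 1059 (region counts, SAP 10.8.1).
- Proportion with a moderate/severe event over 24 weeks: 15–40% (assumption).
- k = 1, 3 or 5 affected deaths, all in one arm (assumption, worst case).
- Events split equally between arms, so e = D/2, where D is the total number of events.

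Counting the k deaths as events instead of censoring them changes the hazard ratio by a factor of about (e + k)/e. The 95% confidence limits lie a factor of about exp(1.96 × 2/√D) either side of the estimate.

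| Event proportion | D | e | k = 1 | k = 3 | k = 5 | 95% CI factor |
|---|---|---|---|---|---|---|
| 15% | 159 | 79.5 | 1.013 | 1.038 | 1.063 | 1.36 |
| 20% | 212 | 106 | 1.009 | 1.028 | 1.047 | 1.31 |
| 30% | 318 | 159 | 1.006 | 1.019 | 1.031 | 1.25 |
| 40% | 424 | 212 | 1.005 | 1.014 | 1.024 | 1.21 |

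For example, at 20% with k = 3, (106 + 3)/106 = 1.028. Cox models refitted to simulated data gave the same ratios at 20% (1.010, 1.028, 1.047) and 30% (1.006, 1.019, 1.032) to within 0.001. With no such deaths the shift is zero, and deaths spread over both arms largely cancel in the ratio.

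**The case against.** The strongest reply is that the plan is consistent. Protocol 12.7.1.1, the exacerbation-history rule in SAP 10.6.2 and SAP 10.6.4 all grade by treatment and admission. The SAP implements the endpoint the protocol defines, and nothing in the documents requires death to count. This stands as a description: there is no contradiction to reconcile. It does not make the literal result sensible for the affected case.

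Second, the case is narrow. Protocol 12.7.1 requires at least two consecutive days of worsening and tells subjects to make contact after more than 24 hours. An investigator might also decline to call a fatal event mild, since it fits poorly with self-management. Narrowness stands. But no rule directs the investigator to another grade, the SAP's mild definition drops the self-management wording, and the documents do not say whether the derived or the recorded severity prevails.

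Third, the deaths would be visible. Exacerbation outcome is summarised (SAP 8.1.1.2, Table 2.18), a Death section of the eCRF is required for every death (Protocol 7.4.2.4), and deaths receive narratives (Protocol 9.4.4). This also stands, so a reader who infers that such deaths would be hidden goes too far. The serious-adverse-event route is less certain, because Protocol 12.4.2 says an event that is not an adverse event cannot be serious and gives death from disease progression as an example. Visibility elsewhere does not, however, correct the Cox or Kaplan-Meier analysis.

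A reader might also infer from the SAP's duration formula, which can end at the date of death, that fatal exacerbations were foreseen and then left out of the severity rule. The formula does not show that: it is needed for anyone who dies of any cause with an unresolved exacerbation.

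**Conclusion.** The gap is real but minor. Under the literal SAP rule, a fatal on-treatment exacerbation without steroid, antibiotic or admission is mild. If it would have been the subject's first moderate/severe event, it becomes informative censoring.

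It would be tempting to conclude that fatal exacerbations in general are counted as mild and lost. The documents do not support that: admitted cases are severe, cases treated at home are moderate events, and subjects with an earlier event are unaffected. Nor could this plausibly overturn a trial conclusion. The endpoint is secondary and unpowered, with no multiplicity adjustment and no treatment p-values displayed (SAP 10.10.1).

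At event proportions of 20–40% and one to five deaths all in one arm, the hazard ratio moves by 0.5–4.7%. The least favourable corner examined, 15% with five deaths, gives 6.3%. All of these lie well inside confidence limits that are 21–36% either side on the ratio scale. Event rate and death count are assumptions, since the documents state neither. The primary endpoint is essentially untouched because no spirometry follows death.

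**What to change.** Before unblinding, add one sentence to SAP 10.6.4: for analysis, an on-treatment exacerbation with a fatal outcome is classed as severe, with the event at its onset date. Apply it in Tables 2.18 and 2.20 and Figure 2.9, and use the same severity label for post-treatment exacerbations in Table 2.19. State whether it also feeds the data exclusion after a moderate/severe exacerbation in SAP 10.1.2, where it could remove a trough FEV1 taken between onset and death. List it in SAP 2.1 as a change from Protocol 12.7.1.1, since that section currently records only the renaming of the primary analysis population.

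No new data are needed: onset date, outcome and date of death are already used in the SAP. The cost is a small departure from the protocol's severity definition. If the sponsor prefers to keep that definition for the main analysis, the minimum is to pre-specify the reclassification as a sensitivity analysis of time to first moderate/severe exacerbation.

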10.7. Appendix 7: Premature Withdrawals & Handling of Missing Data

10.7.1. Premature Withdrawals

Element	Reporting Detail
General	
 For reporting purposes, subject study completion (i.e. as specified in the protocol) was defined as a subject will be considered to have completed the study when they have completed all phases of the study including screening, run-in, randomization, the randomized treatment phase up to visit 5 and safety follow-up visit. Withdrawn subjects will not be replaced in the study. All available data from subjects who were withdrawn from the study will be listed and all available planned data will be included in summary tables and figures, unless otherwise specified.
Vitals/Lab/ECG	
 Vitals/Lab/ECG data collected as part of the early withdrawal at a scheduled visit, or at a standalone EW visit will be used in the summary of absolute values and change from baseline as part of the ‘minimum post baseline’, ‘minimum change from baseline’, ‘maximum post-baseline’ and ‘maximum change from baseline’ for diastolic and ‘maximum post-baseline’ and ‘maximum change from baseline’ for pulse rate and systolic blood pressure

10.7.2. Handling of Missing Data

Element	Reporting Detail
General	
 Missing data occurs when any requested data is not provided, leading to blank fields on the collection instrument : 
 These data will be indicated by the use of a “blank” in subject listing displays. Unless all data for a specific visit are missing in which case the data is excluded from the table. Answers such as “Not applicable” and “Not evaluable” are not considered to be missing data and should be displayed as such. No imputation will be made for any missing numerical data, except in the sensitivity analysis of the primary endpoint to assess the impact of missing data on study results. Missing data will generally not be considered in the calculation of percentages (i.e., the denominator will not include subjects who have missing data at a given time point).
Responder	
 Subjects with a missing baseline will have responder status as missing. Subjects with missing post-baseline data and a subsequent non-missing assessment will not be considered a responder or non-responder but will be left as missing. Subjects with a baseline but all missing post-baseline data will be considered a non-responder at all time points.

10.7.2.1. Handling of Missing or Partial Dates

Element	Reporting Detail
General	
 ● Partial dates will be displayed as captured in subject listing displays. ● Dates which are completely missing will not be imputed, with the exception of the treatment stop date. Details around imputation of the treatment stop date are provided in Section 10.6.1
Concomitant Medications	
 ● Partial dates for any concomitant medications will be imputed using the following convention: 
 ○ If the partial date is a start date, a '01' will be used for the day and 'Jan' will be used for the month ○ If the partial date is a stop date, a '28/29/30/31' will be used for the day (dependent on the month and year) and 'Dec' will be used for the month. ● The recorded partial date will be displayed in listings.
Adverse Events, Exacerbation, Pneumonia	
 ● Any partial dates will be imputed using the following convention: 
 ○ If the partial date is a start date, a '01' will be used for the day and 'Jan' will be used for the month. ○ However, if these results in a date prior to Week 0 and the event could possibly have occurred during treatment from the partial information, then the Week 0 date will be assumed to be the start date. ○ The event will then be considered to start on-treatment (worst case). ○ If the partial date is a stop date, a '28/29/30/31' will be used for the day (dependent on the month and year) and 'Dec' will be used for the month. ○ The recorded partial date will be displayed in listings.

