6. STUDY TREATMENT

6.1. Investigational Product and Other Study Treatment

The term 'study treatment' is used throughout the protocol to describe any combination of products received by the subject as per the protocol design. Study treatment may therefore refer to the individual study treatments or the combination of those study treatments.

All treatments will be delivered by ELLIPTA containing 30 doses.

Following the run-in period, eligible subjects will be randomized (1:1) to one of the following double-blind treatment groups:

- FF/UMEC/VI 100mcg/62.5mcg/25mcg and placebo, both via the ELLIPTA once daily in the morning
or,
- FF/VI 100mcg/25mcg and UMEC 62.5mcg, both via the ELLIPTA once daily in the morning.

The randomisation will be stratified based on long-acting bronchodilator usage during the run-in (none, one or two long-acting bronchodilators per day).

The ELLIPTA contains 30 doses (FF/UMEC/VI, FF/VI, UMEC or placebo). Each subject will be instructed on the proper use of the ELLIPTA and will inhale once from each of their ELLIPTAs each morning for the duration of the 24-week treatment period. Subjects will self-administer their first dose of blinded study treatment in the clinic during Randomisation (V2). On the morning of the other study clinic visits, subjects will refrain from taking their morning dose of study treatment until instructed to do so by clinic personnel. Subjects will take their last dose of study treatment at the clinic at Visit 5 and a safety follow-up will be conducted either by phone call or clinic visit approximately one week later. Subjects will discontinue their existing COPD medication on the day before Randomisation (V2) but may continue their study-supplied rescue albuterol/salbutamol.

There are no plans to provide the study drug for compassionate use following study completion.

Descriptions of the study treatments administered via the ELLIPTA are provided in [Table 2](#).

Table 2 Description of study treatment inhalation powder via ELLIPTA

FF/UMEC/VI	First strip	Second strip
		FF blended with lactose
Dosage Form	ELLIPTA with 30 doses (2 strips with 30 blisters per strip)	
Unit Dose Strengths	100mcg per blister	62.5 mcg per blister UMEC, 25 mcg per blister VI
Physical description	Dry white powder	Dry white powder
Route of Administration	Inhaled	
FF/VI	First strip	Second strip
	FF blended with lactose	VI blended with lactose and magnesium stearate

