6.10.2. Prohibited Medications and Non-Drug Therapies

Medications prohibited at specific time intervals prior to Visit 1 (and at any time during the study) are identified in the Exclusion Criteria (Section 5.2).

NOTE: All COPD medications (except for rescue albuterol/salbutamol, mucolytics and oxygen) are prohibited during the randomised period of the study except during the treatment of a moderate/severe COPD exacerbation or pneumonia. In the event of an exacerbation or pneumonia, sites should attempt to follow protocol treatment guidelines (Section 12.7); however, treatment with any medication that the health care provider deems necessary is allowed. Caution is advised in using a LABA or LAMA to treat a subject currently taking study treatment as these additional medications may increase the risk of overdose. If necessary the investigator or other health care personnel may stop the

subjects study treatment temporarily in order to treat the COPD exacerbation. Subjects who require more than two consecutive 14 day courses of treatment (i.e. antibiotics or corticosteroids) should be evaluated for their continuation on study treatment by the investigator in consultation with the GSK medical monitor.

Eligible subjects will be allowed to continue their usual COPD medications during screening and the 2-week run-in period. On the morning of the Screening Visit subjects will refrain from taking their morning dose of their usual COPD medications until instructed to do so by clinic personnel. During the run-in period subjects will continue to use their usual COPD medications with no change in medication or dose.

The number of long-acting bronchodilators taken each day during the run-in period (0, 1 or 2) will be recorded.

On the day before the Randomisation Visit (V2), subjects will take their last dose of their usual COPD medications and will not use any other COPD medications (except for those allowed per protocol: rescue albuterol, oxygen, mucolytics and medications for the treatment of a COPD exacerbation or pneumonia) until the end of the study. Rescue albuterol/salbutamol can be used throughout the study as needed but must be withheld for at least 4 hours prior to conducting spirometry.

COPD Medications and non-drug therapies that are prohibited during the randomized portion of the study:

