10.4.1. Treatment Phase for Concomitant Medication Data

COPD medication combinations taken at screening will include all COPD medications that were taken on the day of the screening visit, excluding medications that stopped on the day of the screening visit. Calculation of stratum, i.e. long-acting bronchodilator usage per day during the run-in (none, one or two long-acting bronchodilators per day), will also be based on the COPD medication taken on the day of the screening visit. If the calculated stratum is different to the randomized stratum, the calculated stratum will be used as a covariate in all analyses, but both values will be listed. Treatment phases for summaries of COPD and non-COPD concomitant medications will be defined as follows:

Definition	Treatment Phase		
	Run-in	On-treatment	Post-treatment
Subject did not take study treatment (e.g. run-in failures) and conmed stop date > date of Screening or variable that asks if conmed is ongoing (refer hereafter as goingmed) is “yes”	Y		
(Conmed start date < treatment start date or variable that asks if medication taken prior to study is “yes” (refer hereafter as priormed)) and date of Screening < conmed stop date < treatment start date	Y		
(Conmed start date < treatment start date or priormed is yes) and treatment start date ≤ conmed stop date ≤ treatment stop date	Y	Y	
(Conmed start date < treatment start date or priormed is yes) and (conmed stop date > treatment stop date or goingmed is “yes”)	Y	Y	Y
(Treatment start date ≤ conmed start date < treatment stop date and treatment start date ≤ conmed stop date ≤ treatment stop date) or (Treatment start date = conmed start date = conmed stop date = treatment stop date)		Y	
([Treatment start date ≤ conmed start date < treatment stop date] or [Treatment start date = conmed start date = treatment stop date]) and (conmed stop date > treatment stop date or		Y	Y

Definition	Treatment Phase		
	Run-in	On-treatment	Post-treatment
goingmed is Yes)			
Conmed start \geq treatment stop date and treatment start date \neq treatment stop date			Y

NOTES:

- A concomitant medication will be classed in every period of the study in which it was taken (e.g., run-in, on-treatment or post-treatment).
- See Section 10.7.2.1 for handling of partial dates.
- If the study treatment stop date is missing, it will be imputed as described in Section 10.6.1.
- Medications that stopped prior to Screening will not be assigned a treatment phase and will not be summarized.

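### Partial stop dates are imputed to month-end or December without using dates the study already holds, which can lengthen exacerbations, class stopped COPD drugs as on-treatment and alter the derived stratum

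*SAP*

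**What the plan says.** SAP 10.7.2.1 gives the same stop-date rule twice, once for concomitant medications and once for adverse events, exacerbations and pneumonia: "If the partial date is a stop date, a '28/29/30/31' will be used for the day (dependent on the month and year"), with December when the month is also missing. Neither version sets an upper limit. The event start-date rule does have a bound: if the imputed start falls before Week 0 but the event could have begun on treatment, "then the Week 0 date will be assumed to be the start date". Wholly missing dates are outside the issue: "Dates which are completely missing will not be imputed, with the exception of the treatment stop date".

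Three other parts of the plan use these dates.

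- **Medication phases (SAP 10.4.1).** A drug begun before treatment is Run-in only if "date of Screening < conmed stop date < treatment start date". It is Run-in and On-treatment if "treatment start date ≤ conmed stop date ≤ treatment stop date". The notes to that table send partial dates to 10.7.2.1. Protocol 6.10.2 says that on the day before randomisation (V2) "subjects will take their last dose of their usual COPD medications", and Protocol 6.1 gives the same timing.
- **Stratum (SAP 10.4.1).** The number of long-acting bronchodilators is derived from COPD drugs taken on the day of Screening. Where the derived and randomised strata differ, the derived one is the covariate in all analyses.
- **Exacerbation duration (SAP 10.6.4).** "The duration of the exacerbation will be calculated as (exacerbation resolution date or date of death - exacerbation onset date + 1"). The SAP does not say which end date prevails and sets no limit at last contact.

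**The concern.** Taking the latest possible stop date is a common convention. Here it overlooks facts that the database already contains: the first dose date, the study conclusion date and any date of death.

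Table 1.34 summarises on-treatment COPD drugs given for reasons other than an exacerbation. It is where a reader would look for prohibited maintenance therapy during the randomised period, and it could show such use in subjects who stopped on the day the protocol sets. The duration summary could contain values longer than the time the subject was in the study. The stratum derivation is the one written route from this rule into the statistical models.

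**Working it through.** The plan states no figure that depends on this rule, so there is none to reproduce. The check applies the written rules.

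**Inputs.** Stop-date rule from SAP 10.7.2.1; phase table from SAP 10.4.1; duration formula from SAP 10.6.4; last usual COPD dose at V2 minus 1 day (Protocol 6.1, 6.10.2); 24 weeks of treatment plus about 1 week to last contact. Assumptions for illustration: V2 on each of the 365 dates of 2017, treatment stop = V2 + 168 days, last contact 7 days later.

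**1. Usual COPD drug stopped at V2 − 1**

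- Complete date (control): Run-in only for 365 of 365. The phase table works when the date is complete.
- Day missing: if V2 is on day 2 or later of a month, the true stop is in the same month and month-end is on or after V2, so the drug becomes Run-in and On-treatment. If V2 is on the 1st, the true stop is the last day of the previous month and the imputation is exact. That gives 365 − 12 = 353 of 365 (96.7%) misclassified.
- Size of the shift: summing L(L − 1)/2 over month lengths L gives 7 × 465 + 4 × 435 + 378 = 5,373 days. This is 5,373/365 = 14.7 days on average over all dates, or 5,373/353 = 15.2 days over the misclassified ones; the maximum is 30.
- Only the year known: 364 of 365 become On-treatment, and 195 of these are also Post-treatment. The exception is V2 on 1 January.

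**2. Drug stopped before Screening**

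Protocol 6.10 collects COPD drugs from about 3 months before Screening, so drugs already stopped can be in the data. Suppose a long-acting bronchodilator stopped earlier in the Screening month and the day is missing. Month-end falls after Screening unless Screening is on the last day of the month, so the drug is read as current. SAP 10.6.2 combines none and one bronchodilator into one category. The covariate therefore changes only if the extra drug takes the subject's count to two.

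**3. Exacerbation duration (resolution − onset + 1)**

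Example: onset 28 May, true resolution 6 June, last contact 9 June.

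| Resolution recorded as | Date used | Duration (days) | Days past last contact |
|---|---|---|---|
| Complete | 6 June | 10 | none |
| Day missing | 30 June | 34 | 21 |
| Year only | 31 December | 218 | 205 |
| Year only, limited to last contact | 9 June | 13 | 0 |

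Onset on 10 March with a year-only resolution gives 22 days in March + 275 from April to December = 297 days. A subject who completes is in the study for about 25 × 7 = 175 days after randomisation.

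A simulation of 200,000 events gives a sense of frequency among partial dates. It assumes a mean true duration of 12 days, onset uniform over days 0 to 159 and study conclusion on day 175; none of the three is a planned figure. The mean overstatement was 14.7 days with the day missing and 182 days with only the year known. The imputed date passed study conclusion in 6% and 76% of cases respectively.

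**4. Does one limit cure both problems?**

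No. Limiting the date to last contact removes the duration overrun but leaves 353 of 365 drug records misclassified. The drug problem needs its own rule tied to Week 0.

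**The case against.** The strongest reply is that partial dates should be uncommon where they would matter most. The last usual COPD dose falls on a day fixed by the protocol. Dates of administration are a minimum recording requirement (Protocol 6.10). Onset and resolution dates must be recorded for every exacerbation (Protocol 12.7.1.5), and medications and exacerbations are reviewed at each visit. The 96.7% applies only once a date is known to be partial, and a year-only resolution of an on-study exacerbation is hard to imagine. Listings also show the date as recorded. All of this stands and limits the point to a minor one.

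An end date after last contact can also be genuine. Serious adverse events are followed to resolution or stabilisation (Protocol 7.4.2.3), and an exacerbation meeting that definition is recorded as one (Protocol 12.7.1.1). A limit that overrode a recorded later month would therefore be wrong. Removing uncertain drugs from Table 1.34 altogether could likewise hide real prohibited use.

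Four stronger readings are tempting, and the documents do not support them:

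- *That FEV1 data would be dropped from the primary analysis.* The prohibited-medication exclusion in SAP 10.1.2 is set by the Protocol Deviation Management Plan, which is not among the documents. Nothing says that it uses these phases or imputed dates.
- *That every partially dated exacerbation is overstated.* One that truly resolved on the last day of the month is not, if only the day is missing.
- *That durations generally run past death.* SAP 10.6.4 already offers the date of death as an end date. An overrun needs a partial resolution date to be used in its place.
- *That time to first exacerbation is affected.* It uses onset dates.

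**Conclusion.** The point holds as a minor defect in a data rule. As written, SAP 10.7.2.1 can produce exacerbation durations that exceed observed time. It classes a usual COPD drug stopped at V2 − 1 with the day missing as on-treatment for 353 of 365 V2 dates. It can also count a bronchodilator stopped before Screening in the derived stratum. The first two effects are confined to descriptive tables: duration in Tables 2.18 and 2.19, and Table 1.34 (also Table 1.35 for year-only dates). The third reaches the models, but only for subjects whose category changes, and the effect on the treatment estimate is likely to be negligible.

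The counts assume a 365-day year and a 168-day treatment period and are conditional on the date being partial. The documents do not give the share of partial dates, so the number of affected records is unknown and probably small. No between-arm bias is shown.

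**What to change.** 1. In SAP 10.7.2.1, set an imputed stop date no later than the study conclusion date or date of death whenever the recorded part of the date is compatible with that limit. Leave a recorded later month or year under the present rule. Keep these events in the duration summary.
2. In Table 1.34, put COPD drugs started before Week 0 whose partial stop date is compatible with stopping before Week 0 on a separate line, *on-treatment use uncertain*, and flag them in Listing 28. Do not count them as on-treatment, and do not drop them.
3. Where Screening-day use of a long-acting bronchodilator depends on an imputed stop date, use the randomised stratum in the models instead of the derived one.

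The cost is a few sentences in the SAP, a small change to the date derivation and one extra table line. One imprecision remains: an event that truly resolved after last contact, but whose partial date is compatible with the limit, will be shortened.
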